**Work-related attention bias modification training and virtual reality training in
occupational rehabilitation: A multisite pilot study**

Project responsibility

[name], Norwegian National Advisory Unit on Occupational Rehabilitation

Project manager

[name], Norwegian National Advisory Unit on Occupational Rehabilitation

[name], Norwegian National Advisory Unit on Occupational Rehabilitation

Project coworkers' Work-related attention training

[name], Idrettens Helsesenter

[name], Betania Malvik

[name], Unicare Fram

[name], Physical Medicine and Rehabilitation, Outpatient Department Bodø.

[name], Norsk Arbeidshelse

[name], Hæfi Rehabilitering, Island

Project coworkers' Virtual reality

[name]/[name], Muritunet

[name], Red Cross Haugland Rehabilitation Centre

[name], The Rehabilitation Centre AiR

STUDY PROTOCOL

BACKGROUND

Individuals on sick leave can be offered work-related rehabilitation with the main aim to return to part or full time work. This multisite pilot study seeks to investigate the effect of a possible new intervention called attention bias modication (ABM). Patients will be recruited from both inpatient and outpatient clinics in the regional health authorities Mid and South-East. The cognitive psychological approach will be adopted, investigating changes in the cognitive function attention during rehabilitation for patients sick listed due to psychological and musculoskeletal disorders and whether the changes can predict return to work (RTW) and employment status.

More than 600 000 Norwegians between 18 and 64 years remain outside the labour market and receive health-related benefits (Øverland et al., 2011). Psychological and musculoskeletal disorders are the most common causes of sickness absence (OECD, 2010; Brage et al., 2010; Knudsen et al., 2012; Mykletun et al., 2009) and anxiety and depression alone constitute one third of all disability pensions in Norway (Mykletun & Knudsen, 2009) and in the OECD countries (OECD, 2003). Given the prevalence of common psychological disorders such as anxiety and depression (Mykletun et al., 2009) work-related rehabilitation has proven to be a successful intervention in helping individuals with anxiety and depression and musculoskeletal disorders to RTW (Gismervik et al., 2020). The aim of work-related rehabilitation to increase the likelihood of sustainable RTW. The programmes are commonly tailored to improve the patients' level of functioning and work ability with an emphasis on physical activity, cognitive treatment components such as cognitive behavioural therapy and collaboration with the workplace. The main aim of all activities is to improve the person's self-efficacy, self-esteem and coping related to family and working life. Often an interdisciplinary team work in collaboration with the patient and are commonly made up of psychologists, physicians, nurses, physiotherapists, job specialists and sport educators.

The application of cognitive psychology to the investigation of psychological disorders has increased in recent years. Cognitive impairments and biased processing of emotional information

have been found in depression and anxiety (Beblo et al., 2011; Landrø & Andersson, 2012) and musculoskeletal and chronic pain (Apkarian et al., 2004; Landrø et al., 2013). Participation in the working life is generally considered to have beneficial effects on psychological health (Lau et al., 2012) and cognitive and emotional factors seem prerequisites for a productive working life (Fisher et al., 2017; Rodriguez et al., 2020). Occupational competence requires cognitive skills both at a personal, emotional and workplace level (Pompeii et al., 2005; Shaw & Lysaght, 2008). Preliminary research findings for the patient groups seeking work-related rehabilitation point to an association between improvements in cognitive functions and a reduction in sick leave (Johansen et al., 2019; 2021).

Attentional bias

Our attentional system is thought to be automatically drawn to particular somatic stimuli or environmental situations (Yiend, 2010). In experimental paradigms seeking to elucidate the mechanisms behind attentional processing of emotional information, the ability to recognise and recall facially, vocally and bodily expressed emotions, smells and emotion words and pictures, is investigated. One robust finding related to anxiety is that individuals vulnerable to anxious states are thought to attend to material of negative content as opposed to positive content (Williams et al., 1997; Yiend, 2010). This would involve fear-relevant material for the generalised anxiety individual and socially threatening information for the social phobia individual. What characterises anxiety is the bias or even priority in attentional resources given to threat over other stimuli. This effect has been named emotion-congruent attentional biases because individuals will often attend to emotional information and situations in the environment that matches the individuals' emotional characteristics. Similarly, depressed individuals will allocate more attention towards negative thoughts and information, which suggests that negative information is more readily recollected than positive information (Yiend, 2010). Deficits in emotion processing are thought to play both a causal and maintaining role to conditions such as anxiety and depression (Yiend, 2010).

A concept that is interlinked with attentional bias is cognitive appraisal. It plays a crucial role in emotional experience and was first proposed by Lazarus (1982). Three specific forms of appraisal have been postulated:

1. Primary appraisal (an environmental situation is regarded as being positive, stressful or irrelevant to well-being).
2. Secondary appraisal (account is taken of the resources that the individual has available to cope with the situation).
3. Re-appraisal (the stimulus situation and the coping strategies are monitored, with the primary and secondary appraisals being modified if necessary).

The concept of cognitive appraisal lends itself readily, similarly to attentional bias, to better understand the complaints reported by patients in work-related rehabilitation. The perception and experience of subjective health complaints and musculoskeletal and chronic pain have provided similar insight into attentional biases and dysfunctional appraisals as demonstrated in anxiety and depression (Brosschot, 2002; Hayes et al., 2010; Pincus & Morley, 2001). For example, it has been revealed that patients selectively process pain-related information, interpret ambiguous stimuli as pain stimuli and better remember details of pain behaviour. This suggests dysfunctions in attention (bias) and emotional states (Eccleston & Crombez, 1999; Pincus & Morely, 2001) and confirms the close relationship between appraisal, on the one hand, and experienced emotions such as anxiety, depression, pain on the other hand.

Computerised cognitive training has become a widespread intervention to improve attention and memory. Virtual reality (VR) is a measure that falls under the cognitive approach as VR technology provides the opportunity to expose participants to what hinders them from participating in working life, as well as improving attention and concentration which increases mental capacity. Previous research has shown that VR, used as an emotion-focused distraction method, reduces symptoms of anxiety, depression, fatigue and pain compared to treatment as usual (Ioannou et al., 2020). Exposure therapy using VR for social anxiety has proven to be effective both immediately after

treatment and during long-term follow-up, although long-term effects after in vivo exposure therapy appear to have a slightly better effect (Horigome et al., 2020). We assume that VR also improves rehabilitation components aimed at various forms of exposure, work training, strengthening of attention and stimulation of movement and activity despite health problems, which in the long run increases the chances of returning to work.

To target the appraisal mechanisms and emotion experiences the attention bias modification task (ABM) was developed (Browning et al., 2012). Several Norwegian studies have documented that ABM training has the potential to modify attentional biases in depression (Jonassen et al., 2019) and anxiety (Kraft et al., 2019) as well as increasing motivation for daily life activities (Kraft et al., 2019). The ABM has also been used in combination with acceptance and commitment therapy in persons reporting depressive symptoms (Østergaard et al., 2019). The combination of ABM and ACT and ACT alone similarly decreased depressive symptoms after treatment and during follow up. Cognitive training has been shown to improve the specific cognitive functions targeted in the training, however the degree to which effects generalize to working life and daily life functions is still questioned (Melby-Lervåg, 2016).

The quantitative aim of this pilot study is to compare VR training and ABM training to investigate whether the different training forms result in different results measured with work-related outcomes and cognitive outcomes. The qualitative aim of this pilot study is to investigate the patients' experiences with the usage of VR.

Objectives - quantitative

The objective of this study is to investigate whether VR and ABM training increases work ability, work-related self-efficacy, attention and reduces symptoms of depression and anxiety and consequently change an attentional bias from negative to positive stimuli. We will compare patients receiving work-related interventions + VR, work-related interventions + ABM training and work-related interventions only. We will also investigate whether positive changes in attentional bias are

associated with increased work participation. Self-reported work ability, self-efficacy, depression, anxiety and objective computerised cognitive and emotional testing will be assessed at baseline (start rehabilitation/treatment) and at posttest (end rehabilitation/treatment).

Objectives - qualitative

The objective of this part is to investigate the experiences in using VR. R&D personell will make individual interviews with five patients at each of the three clinics involved in piloting VR. The aim of the interviews will be to capture how the patients experienced the VR activity, the demands of the VR activity, how VR has influenced different aspects of health and whether VR has influenced the abilities to return to work.

STUDY PLAN

Individuals eligible for inclusion will be those between 18 – 67 years, on sick leave, work assessment allowance, disability pension receiving work-related rehabilitation or treatment at seven clinics with either an ICPC-2 (International Classification of Primary Care, Second edition) within the L (musculoskeletal), P (psychiatric) or A (unspecific disorders) categories or ICD-10 diagnosis within the F (mental and behavioral disorders), M (Diseases of the musculoskeletal system and connective tissue) or other diagnoses. *Exclusion criteria:* 1) Applying for full disability pension; 2) Unable to complete the measures and receive instructions in Norwegian.

Design and sampling

This is a non-randomised controlled experiment where we aim to recruit 20 patients from each of the six clinics involved in ABM training and up 100 from each of the clinics involved in VR. That is, 10 receiving ABM training and 10 in the control group, and 60 receiving VR and 40 in the control group. The participants will complete the questionnaires and cognitive measures one the day of arrival and on the penultimate or ultimate day of the rehabilitation/treatment. The measures will take

approximately one hour to complete at each measurement point and will not interfere with the participation in the rehabilitation/treatment.

In the qualitative part of this pilot, it is aimed to recruit 15 patients, five at each of the three clinics.

Self-reported questionnaire measures

Kvalitetsregisterkjema fra Nasjonal kompetansetjeneste for arbeidsrettet rehabilitering

Work Ability (Ahlstrom et al., 2010)

Return to work self-efficacy (Gjengedal et al., 2021; Nøttingnes et al., 2019)

Expectation about return to work (Løvvik et al., 2014)

Hospital Anxiety and Depression Scale (Zigmond & Snaith, 1983)

Computerised cognitive and emotional measures

Rapid Visual Information Processing (Cambridge Cognition, 2020) (**VR group and ABM group**)

Spatial Working Memory (Cambridge Cognition, 2020) (**VR group and ABM group**)

Stop Signal Task (Cambridge Cognition, 2020) (**VR group and ABM group**)

Attention Bias Assessment Task (Browning et al., 2012) (**ABM group only**)

Qualitative measures

Interview guide (National Advisory Unit on Occupational Rehabilitation, 2022)

Primary outcome measure

1) Work ability and expectations to return to work

2) Depression and anxiety

Secondary outcome measures

2) Cognitive and emotional performance assessed with the computerised measures

3) Total number of days on health related benefits in the year after rehabilitation/treatment

4) Patients's experiences in using VR

Virtual reality training

In collaboration with the participating clinics a systematic VR activity plan will be developed. This includes the selection of games and designing a plan that is interesting and motivating both for patients and clinicians.

Attention Bias Modification Training

The ABM task is a computerised, validated visual dot-probe procedure (Browning et al., 2012). In the original version from Browning et al. (2012) paired images of faces (the stimuli) were presented followed by one or two dots (a probe), which appeared behind one of the stimuli. Participants were required to press one of two buttons as quickly as possible to indicate the number of dots in the probe. Stimuli were pictures of emotional faces of three valences: positive, neutral, or negative (angry and fearful). The task comprised 96 trials with equal numbers of the three stimulus pair types. There were equal numbers of trials in which the stimuli were randomly presented for 500 or 1.000 milliseconds before the probe was displayed. Stimuli from two valences were displayed in each trial in one of the following pairing types: positive-neutral, positive-negative, and negative-neutral. Probes were located behind positive (valid) emotional stimuli in 87% of the trials in the training condition. Thus, when completing training, participants should learn to orient attention toward positive stimuli and in this way develop a positive attentional bias.

The aim of the current pilot study is to replace the facial stimuli with work-related stimuli categorized as positive, neutral and negative. We will follow the dosage and frequency of training applied in the other Norwegian studies (Kraft et al., 2019; Jonassen et al., 2019; Østergaard et al., 2019). Participants will use tablets with the ABM task pre-installed and will be instructed to complete

two training sessions every day from Monday to Friday for the duration of the rehabilitation/treatment.

Procedure for recruitment and testing

1. Local project representative hands out the information sheet to newly arrived participants and gives a short explanation about the project
2. The representative meets the participants the following day and asks whether he/she wants to participate. If the participants volunteers, he/she signs the consent form
3. Test 1: During the next two days the participants is administered three attention tests in front of a computer screen. It takes about 30 minutes to complete the tests. The participants also complete questionnaires about their work and health situation, as well as background information such as your age, education, marital status, type of job and work and benefit situation. It takes about 30 minutes to complete the questionnaires.
4. Test 2: On the third or second but last day of rehabilitation/treatment the participant completes the same tests and questionnaires as described above.
5. In the period between test 1 and test 2, all participants undergo VR activities or attention bias modification training on an Ipad/tablet. Each training session lasts for about 15 minutes and is carried out twice a day from Monday to Friday during rehabilitation/treatment or adjusted according to patients' needs and capabilities as well as the already existing rehabilitation programme at each participating clinic.
6. The participants in the control group complete test 1 and 2 but do not receive the added intervention described in 5.
7. R&D personell at each of the three clinics using VR will approach participants each after test 2 (sequence number 4) asking them if they would like to volunteer to take part in an interview about the experiences in using VR.

Power

A priori power calculations for F tests using G*Power (Faul et al., 2007) were performed to check which sample size was required to detect differences between groups in scores on work and health questionnaires using repeated-measures analysis of variance (pretest to posttest changes). Results indicated that with a power of 0.90, moderate effect size set at 0.25 and a two-tailed alpha level of 0.05 (Cohen, 1988), the total number of participants needed would be 44 in each group.

Study period

1 January 2022 to 1 June 2026.

Main study

This pilot study will inform whether we need to make adjustment or changes to the main study expected to commence 1 August 2024 and with particular reference to the following criteria:

- Is the main study feasible
- What changes should be made to the protocol of the main study
- What specific changes and amendments should be made to the design of the main study
- What specific recommendations to the main study are provided by the collaborating clinics and how do we deal with them and implement them in the main study

Dissemination

A project report will be published on www.arbeidoghelse.no. Publication of one scientific article.

Ethical perspectives

The project is approved by the Regional Committee for Medical and Health Research and Sikt – Norwegian Agency for Shared Services in Education and Research.

Gender issues

The participants recruited into the three groups will be matched according to gender.

Funding

This project is self-funded by each participating institution.

REFERENCES

Apkarian, A. V., Sosa, Y., Krauss, B. R., Thomas, P. S., Fredrickson, B. E., Levy, R. E., Norman Harden, R., & Chialvo, D. R. (2004). Chronic pain patients are impaired on an emotional decision-making task. *Pain*, 108, 129-136.

Brosschot, J. F. (2002). Cognitive-emotional sensitization and somatic health complaints. *Scandinavian Journal of Psychology*, 43, 113-121.

Cambridge Cognition. (2020). CANTAB (www.camcog.com). Cambridge Neuropsychological Test Automated Battery. Cambridge, UK.

Cohen, J. (1988). *Statistical power analysis for the behavioral sciences* (2 utg.). Hillsdale: Lawrence Erlbaum Associates.

Eccleston, C., & Crombez, G. (1999). Pain demands attention: A cognitive-affective model of the interruptive function of pain. *Psychological Bulletin*, 125(3), 356-366.

Fisher, G. G., Chaffee, D. S., Tetrck, L. E., Davalos, D. B., & Potter, G. G. (2017). Cognitive functioning, aging, and work: A review and recommendations for research and practice. *Journal of Occupational Health Psychology*, 22(3), 314-336.

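### Does the reference to seven clinics in the inclusion criterion conflict with the six ABM and three VR clinics in a way that needs a change?

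*Protocol*

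**What the plan says.** Under STUDY PLAN, the inclusion criterion covers patients of working age on health-related benefits who are "receiving work-related rehabilitation or treatment at seven clinics". The clinics are not named there.

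Design and sampling, which follows directly, sets the recruitment targets: "20 patients from each of the six clinics involved in ABM training" and "up 100 from each of the clinics involved in VR". At each ABM clinic the split is 10 trained and 10 control; at each VR clinic it is 60 and 40. That sentence gives no number of VR clinics, but three other places do:

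- Objectives - qualitative: "five patients at each of the three clinics involved in piloting VR"
- Design and sampling, qualitative part: "it is aimed to recruit 15 patients, five at each of the three clinics"
- Procedure for recruitment and testing, step 7: "R&D personell at each of the three clinics using VR"

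The opening page lists project coworkers by institution, six for attention training and three for VR. One of the six is "Hæfi Rehabilitering, Island", that is, in Iceland. The Background gives the catchment as follows: "Patients will be recruited from both inpatient and outpatient clinics in the regional health authorities Mid and South-East".

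**The concern.** An inclusion criterion defines who may be enrolled, so a wrong clinic count in it deserves a check. Six plus three is nine, and a reader cannot tell which seven clinics the criterion means. Because targets are set per clinic, the number of clinics fixes the planned size of the study. If seven were the true number, the total would shrink, and on one split the ABM arm would fall below the 44 per group that the Power section asks for.

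The Icelandic institution adds a second doubt. It lies outside the region named in the Background, and exclusion criterion 2 removes patients who cannot manage the tests and instructions in Norwegian. If that clinic is one of the six, up to 20 planned patients depend on it.

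**Working it through.** **Inputs**

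- Clinics in the inclusion criterion: 7 (STUDY PLAN)
- ABM clinics: 6, with 10 trained + 10 control each (Design and sampling)
- VR clinics: 3 (Objectives - qualitative; Design and sampling; Procedure, step 7), with up to 60 trained + 40 control each (Design and sampling)
- Institutions in both coworker lists: 0 (opening page)
- Required size: 44 per group (Power)

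**Can seven be reproduced?** The number of distinct clinics is 6 + 3 − (clinics running both programmes).

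- No overlap, as the lists show: 6 + 3 − 0 = 9
- Without the Icelandic institution: 5 + 3 = 8
- ABM only: 6; Norwegian ABM only: 5; VR only: 3
- Seven requires an overlap of two: 6 + 3 − 2 = 7. The lists show no shared institution. They are lists of coworkers, not of recruiting sites, so nine is the likeliest count but is stated nowhere.

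**Does any planned number depend on seven?** The targets use only the six and the three.

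| Quantity | Six ABM + three VR | Without the Icelandic institution |
|---|---|---|
| ABM arm | 6 × 10 = 60 | 5 × 10 = 50 |
| VR arm | 3 × 60 = 180 | 3 × 60 = 180 |
| Control | 6 × 10 + 3 × 40 = 180 | 5 × 10 + 3 × 40 = 170 |
| Total (maximum) | 420 | 400 |

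Every arm exceeds 44 in both columns. The Icelandic share is at most 20/120 = 16.7% of the patients at ABM clinics and 20/420 = 4.8% of all. If two clinics did run both programmes, the targets would still add to 6 × 20 + 3 × 100 = 420, provided such a clinic recruits for each programme.

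**If seven were the true count with no overlap**

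| Split | Total | ABM arm | VR arm |
|---|---|---|---|
| 4 ABM + 3 VR | 4 × 20 + 3 × 100 = 380 | 40 | 180 |
| 5 ABM + 2 VR | 5 × 20 + 2 × 100 = 300 | 50 | 120 |
| 6 ABM + 1 VR | 6 × 20 + 1 × 100 = 220 | 60 | 60 |

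Only the first split puts an arm below 44. It contradicts the stated six ABM clinics; the second contradicts both stated counts, and the third contradicts the three VR clinics given in three places.

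**The case for a change.** The best argument for a change is that the number stands in an eligibility rule, in an intact sentence, and disagrees with the text right after it. The Power and Main study sections make this a pilot that must report on feasibility, and recruitment against target is hard to judge if the document carries two clinic counts. The repair would cost a word or two. If the true number were seven, between 420 − 380 = 40 and 420 − 220 = 200 planned patients would disappear.

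The inconsistency itself stands: I found no extraction damage or redaction that would explain it. The rest does not carry far. Feasibility would be judged against the per-clinic targets, which are stated separately and are clear. Fewer clinics would not stop any remaining clinic from reaching its own 20 or 100. The loss of 40 to 200 patients takes the one outlying number as true and sets aside every other count in the protocol; no passage supports it.

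On Iceland, the six ABM clinics match the six listed institutions only if the Icelandic one is counted. Recruitment there is therefore implied, although not stated. The Background sentence then describes the catchment too narrowly, which is again a matter of description. Eligibility criteria apply at every site unless the protocol says otherwise, so the Norwegian-language exclusion needs no separate confirmation for one clinic and does not contradict recruitment there.

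**Conclusion.** This is a clerical slip, probably a count that was not kept in step with the clinic list. The criterion says seven, and the protocol otherwise supports nine: six ABM clinics and three VR clinics. The Background region sentence has a similar looseness if the Icelandic institution recruits. Neither feeds a target, arm size, outcome or power figure. The planned maximum is 420, or 400 without the Icelandic institution, and the ABM arm of 60 or 50 stays above 44 either way.

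This rests on two assumptions: that the repeated counts of six and three are the operative ones, and that the coworker lists reflect the recruiting sites closely enough to rule out overlap. If the second fails and two clinics run both programmes, seven would be correct and the target of 420 would still hold where such clinics recruit for each programme. Site staff know whether their clinic takes part, so the miscount would not alter enrolment. The wording can be tidied whenever the text is next edited, but the plan needs no change on this account.

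### Pooling rehabilitation-only patients from separate ABM and VR clinics, with no clinic term, lets clinic differences in change pass as training effects

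*Protocol*

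**What the plan says.** The only analysis the protocol names is in its Power section, where the calculation is meant to "detect differences between groups in scores on work and health questionnaires using repeated-measures analysis of variance (pretest to posttest changes". The inputs are "with a power of 0.90, moderate effect size set at 0.25 and a two-tailed alpha level of 0.05", and the result is that "the total number of participants needed would be 44 in each group". Clinic, clustering and intraclass correlation are not mentioned.

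Objectives - quantitative sets out the comparison as "work-related interventions + VR, work-related interventions + ABM training and work-related interventions only". Gender issues also speaks of three groups. As written, rehabilitation only is one group.

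Design and sampling describes six ABM clinics with 20 patients each and VR clinics with up to 100 each: "That is, 10 receiving ABM training and 10 in the control group, and 60 receiving VR and 40 in the control group". Procedure step 7 gives the number of VR clinics as three. Allocation is not randomised.

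On differences between clinics, the Background states "Patients will be recruited from both inpatient and outpatient clinics". Procedure step 5 allows training to be fitted to the "already existing rehabilitation programme at each participating clinic". The second test falls at the end of each patient's programme.

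**The concern.** ABM patients come only from ABM clinics and VR patients only from VR clinics, while the controls come from both. If patients in the two clinic sets change by different amounts without any training, a comparison of each training with the pooled controls picks up part of that difference. Such a difference is plausible: inpatient and outpatient programmes differ, and the pre-to-post interval is set by each programme. Matching on gender does not remove it.

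At stake are the questionnaire primary outcomes (work ability, expectations about return to work, depression and anxiety). A clinic difference could be reported as a training effect, or could hide one, in a pilot that is meant to shape a main study.

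**Working it through.** **1. The stated sample size.** For two measurements and the group-by-time test, the noncentrality is λ = f²·N·2/(1 − ρ). With f = 0.25, two groups, ρ = 0 and N = 88, λ = 0.0625 × 88 × 2 = 11 on 1 and 86 degrees of freedom, and power is 0.906. N = 86 gives 0.8999. So 44 per group is reproduced with independent patients. A four-group between-subjects test with ρ = 0.5 also gives 44 per group (N = 176, power 0.904), but it tests average level and not change. Three groups with ρ = 0 would need 35 per group for change. No reading that reproduces 44 contains a clinic allowance.

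**2. Planned layout**, reading the numbers in Design and sampling as per clinic:

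| | ABM clinics (6) | VR clinics (3) | Total |
|---|---|---|---|
| ABM | 60 | 0 | 60 |
| VR | 0 | 180 | 180 |
| Control | 60 | 120 | 180 |

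**3. Bias weights.** Let A and V be the mean changes without training in the ABM and VR clinic sets. The pooled control mean is (60A + 120V)/180 = A/3 + 2V/3. With no training effect:
- ABM − control = A − A/3 − 2V/3 = (2/3)(A − V)
- VR − control = V − A/3 − 2V/3 = (1/3)(V − A)

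This step needs no assumed variance.

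**4. False-positive rate with random clinic effects.** Let clinics account for a share r of the variance in change (total variance 1).
- ABM v pooled control: net clinic weights are 10/60 − 10/180 = 1/9 in each ABM clinic and −40/180 = −2/9 in each VR clinic. Their squares sum to 6/81 + 12/81 = 0.222. The naive variance is 1/60 + 1/180 = 0.0222. True/naive = 1 + 9r.
- VR v pooled control: net weights are −1/18 and 1/9, and their squares sum to 6/324 + 3/81 = 0.0556. The naive variance is 2/180 = 0.0111. True/naive = 1 + 4r.
- Either training v controls of the same clinics, at the planned splits: clinic effects cancel, so true/naive = 1 − r.

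The type I error of a nominal 5% test is 2[1 − Φ(1.96/√ratio)]. The three-group F test was simulated (5,000 trials per value of r).

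| r (assumed) | 2% | 5% | 10% |
|---|---|---|---|
| Three-group F | 0.088 | 0.137 | 0.224 |
| ABM v pooled control | 0.071 | 0.104 | 0.155 |
| VR v pooled control | 0.059 | 0.074 | 0.098 |
| Same-clinic controls | 0.048 | 0.044 | 0.039 |

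At r = 1% the first three are 0.061, 0.061 and 0.055. The F test is affected most because it also contains ABM against VR, which carries the whole clinic-set difference.

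**5. A fixed difference between clinic sets.** If A and V differ by an assumed 0.3 SD of change, ABM v control is biased by 0.20 SD (naive standard error √0.0222 = 0.149; about 27% false positives). VR v control is biased by 0.10 SD (standard error √0.0111 = 0.105; about 16%). For 0.2 to 0.4 SD the ranges are 15% to 43% and 10% to 24%.

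**6. Power within clinics.** Under the two-group, ρ = 0 reading, the implied difference in change is d = √(11 × 2/44) = 0.707 SD. For ABM 60 v 60, λ = 0.5/(1/60 + 1/60) = 15, giving power 0.97 to 0.98 over r = 0 to 10%. For VR 180 v 120, λ = 0.5/(1/180 + 1/120) = 36, giving power above 0.99.

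**The case against.** The strongest reply is that the protocol has no analysis section. The quoted sentence describes a power calculation, and the choice of model terms is commonly left to an analysis plan, which may exist but is not shown. That stands in part: a reader might infer that the protocol rules out a clinic term, and it does not. What it does fix is one control group drawn from two separate clinic sets and a between-group comparison of change. Used together as written, these give a biased contrast.

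A second reply is that Design and sampling gives each training its own controls, and that 44 per group reproduces for two groups and not for three. Same-clinic comparison may therefore be what was meant. It would largely solve the problem, but the protocol nowhere says so, and its objectives name a single rehabilitation-only group.

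Two stronger readings are tempting and fail:
- *The unequal ratios (1:1 and 3:2) are the cause.* With 50:50 in the VR clinics, controls would number 60 + 150 = 210, and ABM minus control would carry 150/210 = 0.71 of the clinic-set difference, more than the planned 0.67. All training against all controls, with the planned ratios, has type I error of 0.043 to 0.049 at r = 1% to 10%. The cause is pooling controls across the two clinic sets.
- *The study is too small.* The planned 60, 180 and 180 exceed 44 per group. Under the two-group, ρ = 0 reading, power was 0.93 or more in every case computed, including ABM against pooled controls at r = 10%.

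It is also fair to say that the main-study criteria concern feasibility and design and set no significance threshold, which limits the consequence.

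**Conclusion.** The concern holds in this form: if each training is compared with pooled rehabilitation-only patients and clinic is left out, the contrasts carry two thirds (ABM) and one third (VR, opposite sign) of any difference in change between the clinic sets. Those weights follow from the planned numbers alone. The error rates do not: about 9% to 22%, 7% to 16% and 6% to 10% rest on an assumed clinic share of 2% to 10%, and at 1% the excess is small. The results also assume the per-clinic reading of the recruitment numbers and that recruitment reaches them. The documents establish the absence of a clinic allowance only for the power calculation, and they show no loss of the stated 90% power.

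**What to change.** State in the protocol or analysis plan that each training is compared with rehabilitation-only patients from the same clinics, by entering clinic as a fixed factor acting on change. In a repeated-measures model this means clinic by time, since a clinic main effect alone leaves the change contrast uncorrected. A clinic term is safer than only restricting the controls, because VR recruitment is only up to 100 per clinic. With assumed realised VR/control splits of 60/40, 60/10 and 20/40 and no clinic term, the VR comparison would still have about 11% type I error at r = 5% and 16% at r = 10%.

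Describe power on the within-clinic contrasts: ABM 60 v 60 and VR up to 180 v 120. First reconcile the clinic count, since the eligibility text says seven while the design text and the list of sites give six plus three. No baseline covariate is needed for this purpose, and its use for change in non-randomised groups is debatable.

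The cost is wording only. With nine clinics the term uses 8 degrees of freedom. With unit residual SD, the nominal standard errors rise from 0.149 to √(1/60 + 1/60) = 0.183 SD for ABM and from 0.105 to √(1/180 + 1/120) = 0.118 SD for VR. Part of that rise is only apparent: at r = 5% the true standard error of the pooled ABM contrast is √(0.0222 × 1.45) = 0.179, against √(0.0333 × 0.95) = 0.178 within clinics.
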